Limited non-randomized evidence of thrombectomy efficacy is available in the published literature. A recently published study, a meta-analysis of 7 early window randomized controlled trials by Campbell et al.¹⁴ has suggested benefit of thrombectomy in patients presenting with infarct core of >100 cc. Campbell et al. demonstrated that although functional independence rates remain very low, these patients continue to benefit from thrombectomy. For infarct core volumes up to 125 cc, the number needed to treat for any benefit remains below 10 for most functional outcomes and less than 5 for any functional improvement. In the light of these recently available evidence, these patients may have a low likelihood of functional independence but could still have better functional outcome than patients treated with medical management only. Thus, the protocol was amended to include these patients in the study. Stringent safety monitoring of mortality and symptomatic ICH is employed to ensure patient safety. The amended inclusion criteria will allow for:

- 1) Assessment of population with CTP/MRP core infarct >100cc
- 2) More generalizability of the study findings
- 3) No dependency on perfusion criteria, which will allow for the population to be treated based on non-contrast CT only. Providing data on the efficacy and safety of thrombectomy selection based on a non contrast CT, which is more readily available, would result in an increased thrombectomy availability to centers without perfusion imaging.

Although no upper limit is specified for infarct core volume measurements on CT or MR perfusion imaging, the infarct size is still expected to be limited, to an extent, given imaging exclusion criteria of “Patients with very large core on non-contrast CT i.e. ASPECTS ≤ 2 ” and

patients with “signs of established infarct and large area of cerebral edema on non-contrast CT”.

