For endovascular patients with Extracranial Occlusions, we will conduct the two-step stopping rules for sICH after we enroll 20 patients in this group and then conduct monitoring after every 10 patients in this group (We expect 10% of patients will have isolated extracranial ICA occlusions, that is, among 280 endovascular patients, around 28 endovascular patients are with extracranial ICA occlusions). Similarly, we assign a weakly informative prior distribution for both π_S^E and π_S^M , that is, a beta distribution with two shape parameters at 0.35 and 0.65, which centers at 0.35 with an effective sample size of 1.

The rule of step 1 for sICH in this group can be pre-determined in the following table.

Find your number of **endovascular patients with Extracranial ICA occlusions** in the left-side column (we provide the table up to 100 patients, but if we enroll more than 100 patients in this group, we will run the algorithm and identify the # of sICHs which will trigger the rule). The step 1 for sICH will be triggered if the number of sICHs is in the range in the right-side column (the range is inclusive):

# of patients with extracranial ICA occlusions	# of sICHs
20	11-20
30	16-30
40	20-40
50	24-50
60	28-60
70	32-70
80	36-80
90	40-90
100	44-100

For mortality,

- 1) **Step 1 for mortality:** check whether the posterior probability that the rate of mortality at Day 90 in one of the endovascular group is $> 40\%$ exceeds the cut-off 0.95. That is, check whether $\Pr\{\pi_m^E > 0.40 \mid \text{data}\} > 0.95$, where the mortality rate in this endovascular group is denoted as π_m^E .

In the event that Step 1 for mortality in one of the endovascular group is triggered, step 2 for mortality in this group will be executed. Otherwise, continue the trial.

- 2) **Step 2 for mortality:** if Step 1 for mortality in one of the endovascular group is triggered, check whether the posterior probability that the mortality rate in this endovascular group is higher than the corresponding medical management by 10% exceeds the cut-off 0.95. That is, check whether $\Pr\{\pi_m^E > \pi_m^M + 10\% \mid \text{data}\} > 0.95$, where the mortality rate in the corresponding medical management group is denoted as π_m^M .

In the event that Step 2 for mortality in one of the endovascular group is triggered, patient enrollment will be placed on hold and a meeting of the DSMB will be conducted to discuss the events and make a determination on the continuation of the trial.

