For endovascular patients with CTP/MRP core volume $\leq 100\text{cc}$, we will conduct the two-step stopping rules for mortality after we enroll 50, 100, 150, 200, and 250 in this group (the maximum number of patients to be enrolled into the endovascular group is 280 and we expect 80% of patients' CTP/MRP core volume will $\leq 100\text{cc}$). We assign a weakly informative prior distribution for both π_m^E and π_m^M , that is, a beta distribution with two shape parameters at 0.4 and 0.6, which centers at 0.4 with an effective sample size of 1.

The rule of step 1 for mortality in this group can be pre-determined in the following table.

Find your number of **patients with CTP/MRP core volume $\leq 100\text{cc}$ in the endovascular group** in the left-side column. The step 1 for mortality will be triggered if the number of deaths is in the range in the right-side column (the range is inclusive):

# of patients with CTP/MRP core volume $\leq 100\text{cc}$ in the endovascular group	# of deaths
50	26-50
100	49-100
150	71-150
200	92-200
250	113-250

For endovascular patients with CTP/MRP core volume $> 100\text{cc}$, we will conduct the two-step stopping rules for mortality after we enroll 20 patients in this group and then conduct monitoring after every 10 patients in this group (We expect 20% of patients' CTP/MRP core volume will $> 100\text{cc}$, that is, among 280 endovascular patients, around 56 endovascular patients

are with CTP/MRP core volume >100cc.). Similarly, we assign a weakly informative prior distribution for both π_m^E and π_m^M , that is, a beta distribution with two shape parameters at 0.4 and 0.6, which centers at 0.4 with an effective sample size of 1.

The rule of step 1 for mortality in this group can be pre-determined in the following table.

Find your number of **endovascular patients with CTP/MRP core volume >100cc** in the left-side column (we provide the table up to 100 patients, but if we enroll more than 100 patients in this group, we will run the algorithm and identify the # of deaths which will trigger the rule). The step 1 for mortality will be triggered if the number of deaths is in the range in the right-side column (the range is inclusive):

# of patients with CTP/MRP core volume >100cc in the endovascular group	# of deaths
20	12-20
30	17-30
40	22-40
50	26-50
60	32-60
70	35-70
80	40-80
90	44-90
100	49-100

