For endovascular patients with Extracranial ICA occlusions, we will conduct the two-step stopping rules for mortality after we enroll 20 patients in this group and then conduct monitoring after every 10 patients in this group (We expect 10% of patients to have isolated extracranial ICA occlusion, that is, among 280 endovascular patients, around 28 endovascular patients are with extracranial ICA occlusions). Similarly, we assign a weakly informative prior

distribution for both π_m^E and π_m^M , that is, a beta distribution with two shape parameters at 0.4 and 0.6, which centers at 0.4 with an effective sample size of 1.

The rule of step 1 for mortality in this group can be pre-determined in the following table.

Find your number of **endovascular patients with Extracranial ICA occlusions** in the left-side column (we provide the table up to 100 patients, but if we enroll more than 100 patients in this group, we will run the algorithm and identify the # of deaths which will trigger the rule). The step 1 for mortality will be triggered if the number of deaths is in the range in the right-side column (the range is inclusive):

# of patients with Extracranial ICA occlusions	# of deaths
20	12-20
30	17-30
40	22-40
50	26-50
60	32-60
70	35-70
80	40-80
90	44-90
100	49-100

These rules only serve as guides and do not substitute for the independent decision-making of the DSMB in the determination of whether the study should be stopped for safety reasons. The decision to stop the study will be made by the DSMB after review of all adverse events based on its own independent decision making. The investigators and the sponsor will not be informed of the interim grouped results.

11. Imaging Core Lab

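### Section 10: two Step 1 mortality tables print 32-60 deaths at n=60, where the stated posterior rule gives 31-60 (one-row error, small effect)

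*Combined protocol and SAP*

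**What the plan says.** Section 10 (Stopping rules or safety triggers for the study) sets a two-step mortality rule. For Step 1 the instruction is to "check whether the posterior probability that the rate of mortality at Day 90 in one of the endovascular group is" above 40%, with a cut-off of 0.95 on that probability. If Step 1 is met, Step 2 asks whether endovascular mortality exceeds medical-management mortality by 10 percentage points, again with posterior probability above 0.95. Only Step 2 puts enrollment on hold and convenes the DSMB.

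The prior for each arm's rate is "a beta distribution with two shape parameters at 0.4 and 0.6, which centers at 0.4 with an effective sample size of 1". For both the core >100cc group and the extracranial ICA group, looks are planned at 20 patients and every 10 after that. The section then says "The rule of step 1 for mortality in this group can be pre-determined in the following table", describes the printed ranges as inclusive, and states: "The step 1 for mortality will be triggered if the number of deaths is in the range in the right-side column".

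For n = 20, 30, ..., 100, both tables print these lower limits: 12, 17, 22, 26, 32, 35, 40, 44, 49.

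Expected group sizes are given as "among 280 endovascular patients, around 56 endovascular patients" for core >100cc and "among 280 endovascular patients, around 28 endovascular patients are with extracranial ICA occlusions". The section closes its rules with: "These rules only serve as guides and do not substitute for the independent decision-making of the DSMB".

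**The concern.** The printed limits move irregularly around n=60. They rise by 4, then 6, then 3, where the neighbouring steps are 4 or 5. As a proportion, the trigger rises from 26/50 = 52.0% to 32/60 = 53.3% and then falls to 35/70 = 50.0%. A fixed posterior cut-off with a weak prior should need a broadly falling proportion as n grows, apart from small rounding effects, so the n=60 cell looked suspect.

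At stake is agreement between a safety rule and the table that would be looked up at a monitoring review. A limit that is one death too high means Step 2 is not opened when the rule says it should be. One of the two tables covers core >100cc. Section 1.3 supports including those patients partly with the assurance that "Stringent safety monitoring of mortality and symptomatic ICH is employed to ensure patient safety".

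**Working it through.** **Inputs, all from Section 10.** Threshold rate 0.40; cut-off 0.95; prior Beta(0.4, 0.6); inclusive ranges, so the lower limit is the trigger.

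**Formula.** With k deaths among n patients the posterior is Beta(0.4 + k, 0.6 + n − k). The trigger is the smallest k for which Pr(rate > 0.40 | k, n) > 0.95.

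**Step 1: reproduce the plan's figures.**

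| n | 20 | 30 | 40 | 50 | 60 | 70 | 80 | 90 | 100 | 150 | 200 | 250 |
|---|---|---|---|---|---|---|---|---|---|---|---|---|
| Rule | 12 | 17 | 22 | 26 | **31** | 35 | 40 | 44 | 49 | 71 | 92 | 113 |
| Printed | 12 | 17 | 22 | 26 | **32** | 35 | 40 | 44 | 49 | 71 | 92 | 113 |

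The sICH tables, checked the same way with Beta(0.35, 0.65) and threshold 0.35, match in every row. Across the three groups there are 23 mortality and 23 sICH entries, and 44 of the 46 reproduce. The two that do not are the same n=60 mortality row, printed twice.

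**Step 2: the n=60 row.** Posterior probability that mortality exceeds 40%:

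- 30 deaths: Beta(30.4, 30.6), 0.9389, not met
- 31 deaths: Beta(31.4, 29.6), 0.9644, met
- 32 deaths: Beta(32.4, 28.6), 0.9804, met

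**Step 3: could a different convention explain 32?**

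- *Another cut-off.* A limit of 32 at n=60 needs a cut-off of at least 0.9644. The printed 35 at n=70 needs one below 0.9528, and 113 at n=250 needs one below 0.9514. The 11 other values of n jointly allow only 0.9497 to 0.9514, which contains the stated 0.95 and excludes 0.9644.
- *Another prior.* Beta(1,1), Beta(0.5,0.5), Beta(0.35,0.65), Beta(2,3) and Beta(4,6) all give 31 at n=60.
- *Another test.* An exact one-sided binomial test at 0.05 also gives 31.

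**Step 4: effect on Step 1.** Only exactly 31 deaths in 60 is treated differently. At a true mortality of 40% the chance of meeting Step 1 at this look is 4.4% by the rule and 2.5% by the table; at 50% it is 44.9% and 34.9%.

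**Step 5: effect on an enrollment hold.** Step 2 must also be met. Assuming 60 medical-management patients in the same group (the plan gives no number), 31/60 endovascular deaths meet Step 2 with at most 16 medical deaths (posterior 0.955; 17 deaths give 0.933). Exact calculation over the looks at 20, 30, 40, 50 and 60 with equal arms, given that n=60 is reached:

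| True mortality, EVT / MM | Hold, table | Hold, rule |
|---|---|---|
| 50% / 43% | 6.30% | 6.33% |
| 50% / 35% | 20.4% | 20.9% |
| 50% / 30% | 33.4% | 34.7% |
| 52% / 20% (largest gap on a grid of EVT 40-65%, MM 5-45%) | 62.2% | 65.4% |

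At the 28% / 43% projected in Section 6.1 there is no practical difference.

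**Step 6: chance that n=60 is reached.** Using a Binomial(280, q) upper tail at 60, with all 280 endovascular patients enrolled:

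- Core >100cc: 29.7% at the expected q = 20%; 0.3% at an assumed 15%; 92.8% at an assumed 25%.
- Extracranial ICA: about 1 in 10^8 at the expected q = 10%.

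**The case against.** The strongest reply accepts the arithmetic and disputes the weight.

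- *The 30% is generous.* It takes full enrollment, but the design can stop at 200 or 380 patients. Table 3 in Section 6.1 reports average numbers randomized of 376 to 426 under the null and uniform-effect scenarios, and 500 to 513 under the heterogeneous ones. With 1:1 allocation and 20% prevalence, the chance of 60 endovascular patients with core >100cc is about 0.01% at 376, 0.3% at 426, 7% at 500 and 10% at 513. These use the average N and are only illustrative. If enrichment selects Group 1 or part of it (core <50cc), recruitment of core >100cc stops altogether. This objection stands: 30% is close to an upper value at the expected prevalence.
- *The extracranial look will in practice not occur.* This also stands. That cell belongs on the correction list but adds nothing to the consequence.
- *The formula naturally governs.* The tables are presented as derived from it, and the plan says the algorithm will be run beyond 100 patients. That is a fair reading, but the same text says Step 1 is triggered by the printed range, so someone using the table literally would apply 32.
- *The harm is limited.* Step 1 only opens Step 2, the n=70 row is correct, and the rules are guides for the DSMB. All true. These points bound the harm but do not make the printed limit agree with the rule.

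A fault in reading the PDF is unlikely, since the same value appears in two separate tables.

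**Conclusion.** The concern holds as a minor error. The n=60 mortality cell in the core >100cc and extracranial ICA tables does not follow from the rule, prior and cut-off in the same section, and no single alternative cut-off reconciles it with the other rows. The discrepancy is one death (51.7% by the rule, 53.3% as printed) and makes the table less sensitive than the rule.

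Weighting the gaps in hold probability by the 30% chance of reaching n=60 gives about 0.01, 0.1, 0.4 and 0.9 percentage points for the four scenarios tabulated. These averages assume full enrollment, 20% prevalence and equal arms; early stopping or enrichment would make them smaller, and a higher prevalence larger. The mismatch itself needs no assumption beyond Section 10.

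**What to change.** Reconcile the n=60 mortality cell in both tables with the stated Step 1 rule, which gives 31-60. Optionally, add one sentence saying whether the posterior rule or the printed table governs if they differ; once the cells agree this is a safeguard only. The cost is two table entries and at most one sentence. The rule, prior, cut-off, look schedule and sample size do not change.

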Appendix A: Minimization Randomization Algorithm

Randomization will be done in the emergency room using a web-based dynamic randomization system. Covariate adaptive randomization is planned to be developed and implemented to balance the distributions of important key baseline variables between the two treatment arms. The key variables include **age (<60, 60-69, 70-79, 80-85 years old), presentation NIHSS (6-9, 10-15, 16-20, >20), center, clot location (M1, ICA), treatment time window (0-8, 9-16, 17-24 hours from onset to randomization time), CTP/MRP core volume (<50cc, 50-100cc, >100cc), presence or absence of target mismatch profile (mismatch ratio ≥ 1.8 & mismatch volume ≥ 15 cc) and hemisphere (right, left).**

The randomization algorithm we are going to implement is the algorithm developed by Pocock and Simon (1975), i.e., minimization method. Through this algorithm, the assignment of a new patient to a treatment group is determined so as to minimize the differences between the groups in terms of these important key baseline variables. Unlike traditional stratified randomization, the minimization method works toward minimizing the total imbalance for all factors together instead of considering mutually exclusive subgroups, that is, we will not creating these mutually exclusive subgroups during the randomization. Therefore, this approach is not restricted by the number of variables and possible combinations of levels of balancing factors.

Details of the minimization randomization algorithm and its implementation

Part I: Specification

This section provides a general framework for a study with the implementation of the minimization algorithm proposed by Pocock and Simon (1975).

Assumptions and Notations:

Assume there are K treatments denoted as T_1, T_2, \dots, T_K with the randomization ratio as 1:1:....:1.

Assume there are S variables to be balanced in the minimization algorithm denoted as X_1, X_2, \dots, X_S .

For the variable X_f , suppose there are Q_f levels and denote the level of X_f as $Z_f \in \{1, \dots, Q_f\}$.

Algorithm:

When a new patient enters to the study, denote the observed level of the variable X_f for this patient as $l_f, f = 1, \dots, S$.

Step 1: Calculate the number of existing patients who are at the same level of the variable X_f as this patient in treatment k , denoted as $N_k(Z_f = l_f), k = 1, \dots, K$. So we can obtain $N_1(Z_f = l_f), N_2(Z_f = l_f), \dots, N_K(Z_f = l_f)$.

Step 2: Regarding to the variable X_f , if we assign this patient to treatment k , we should have $N_k(Z_f = l_f)+1$ patients at treatment k who have the same level of the variable X_f as this patient. We obtain the amount of imbalance which would arise by assigning the patient to treatment k as

$$I_k(Z_f = l_f) = D(N_1(Z_f = l_f), \dots, N_k(Z_f = l_f) + 1, \dots, N_K(Z_f = l_f)).$$

Here, $D(\mathbf{a})$ is a function to measure the amount of variation for any set of non-negative integers \mathbf{a} . Then we can calculate the overall imbalance for all S variables arising when assigning the patient to treatment k by taking a weighted average, that is,

$$G_k = \sum_{f=1}^S w_f I_k(Z_f = l_f), k = 1, \dots, K,$$

where w_f denotes the weight for the variable X_f .

Step 3: Find $k^* = \underset{k}{\operatorname{argmin}} G_k$ and assign the patient to treatment k^* with the highest probability among all treatments.

If we consider variance function for D , according to Freedman and White (1978), the total imbalance arising when assigning the patient to treatment k can be simplified as follow

$$G_k = 2(\sum_{f=1}^S w_f N_k(Z_f = l_f)) / (K - 1) + \text{constant}, k = 1, \dots, K.$$

Therefore, $k^* = \underset{k}{\operatorname{argmin}} \sum_{f=1}^S w_f N_k(Z_f = l_f)$

Part II: Implementation in SELECT2

Two treatment groups: T_1 and T_2 with 1:1 ratio.

	Level	Weight
age	<60, 60-69, 70-79, 80-85 years old	4
presentation NIHSS	6-9, 10-15, 16-20, >20	4
clot location	M1, ICA	3
treatment time window from onset to randomization time	0-8, 9-16, 17-24 hours	3
CTP/MRP core volume	<50cc, 50-100cc, >100cc	2
Target mismatch profiles	mismatch ratio ≥ 1.8 & mismatch volume ≥ 15 cc, mismatch ratio < 1.8 or mismatch volume < 15 cc or both	

hemisphere	right, left	1
center		1

For the first patient to be enrolled, we assign this patient to one of the treatments using equal randomization. Then before we assign next patients, we will calculate G_1 and G_2 , if $G_1 > G_2$, then assign next patient to T_2 with a probability p . Here, we set $p = 0.9$; if $G_1 = G_2$, then assign patient to T_2 with probability 0.5; if $G_1 < G_2$, then assign patient to T_2 with probability $=1-p = 0.1$.

References

Pocock, S.J. and Simon, R., Sequential treatment assignment with balancing for prognostic factors in the controlled clinical trial. *Biometrics*. v31. 103-115.

Pocock, S.J., Allocation of Patients to Treatment in Clinical Trials. *Biometrics*. v35. 183-197

Appendix B. Efficacy and futility bounds for interim and final analysis

At the l th interim analysis, let W_i^l be the sum of the ranks of Rankin scores from the endovascular group in the patient subgroup Π_i , $j = 1, \dots, J$. In our trial, we defined $J = 6$ groups with Π_j denotes the entire patient population and Π_1, \dots, Π_5 denote the subgroups of G1A, G1A+G1B, G1A+G1B +G2A, G1A+G1B +G2A +G2B, G1A+G1B +G2A +G2B +G3A, respectively.

The standardized Wilcoxon statistic for patient subgroup Π_i is

$$Z_i^l = \left\{ W_i^l - \frac{n_i^l(n_i^l + n_{0i}^l + 1)}{2} \right\} / \left\{ \frac{n_i^l n_{0i}^l (n_i^l + n_{0i}^l + 1)}{12} \right\}^{1/2},$$

where, n_i^l and n_{0i}^l denote the numbers of patients enrolled into the endovascular group and medical management group at the l th interim analysis, respectively.

At the l th interim analysis, we will terminate the trial and claims efficacy for the endovascular group if the following efficacy bound is crossed, that is,

$$Z_j^l \geq b.$$

Otherwise, we will proceed to the subgroup selection if the following futility bound is crossed, that is,

$$\widetilde{Z}_j^l \leq \widetilde{b},$$

where

$$\widetilde{Z}_j^l = \left\{ W_i^l - \frac{n_i^l(n_i^l + n_{0i}^l + 1)}{2} - n_i^l n_{0i}^l \theta \right\} / \left\{ \frac{n_i^l n_{0i}^l (n_i^l + n_{0i}^l + 1)}{12} \right\}^{1/2}.$$

When the above criteria is satisfied, a subgroup \hat{I} with the largest value of Z_i^l for $i \neq J$ is chosen. The future enrollment of the trial will include patients of this subgroup only, while the maximum total sample size is still $N=560$.

Similar to testing the efficacy and futility in the entire population, at stage l' , we will terminate the trial and claim efficacy for the endovascular group in this selected subgroup if the following efficacy bound is crossed

$$Z_j^{l'} \geq b.$$

We may also terminate for futility if

$$\widetilde{Z}_j^{l'} \leq \widetilde{b}.$$

If neither the efficacy nor futility bound for the entire population ever occurs, the trial proceeds to the final stage and we terminate the trial and claim efficacy for the endovascular group if

$$Z_j^{l=3} \geq c.$$

Under our design setting (maximum sample size $N=560$ and conducting interim analysis at $N=200$ and $N=380$ with type I error at 0.025 and power at 0.9), we obtain $b = 2.604$, $\tilde{b} = -1.897$, $c = 2.772$ for our efficacy and futility boundaries. We assume θ to be the projected treatment effect given the maximum sample size for testing the hypothesis: $H_0: P(Y \leq X) = \frac{1}{2}$, $H_A = P(Y \leq X) = \frac{1}{2} + \theta$ using the fixed-sample-size test and is calculated as $\frac{(Z_{1-\alpha} + Z_{1-\beta})}{\sqrt{3N}} = 0.0791$. Here, Y denotes the Rankin score in the medical management group and X denotes the Rankin score in the endovascular group. The rationale of this set-up is detailed in section 3.1 of Lai et al (2014).

Reference

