Patients with extracranial ICA occlusion, as of now, do not have a proven treatment for revascularization and the rates of recanalization achieved by the only currently FDA approved treatment, IV tissue plasminogen activator have been poor¹⁸⁻¹⁹. Another issue with these patients is the potential of so called “Pseudoextracranial occlusion.” In a significant proportion

of cases with intracranial ICA occlusion, because of low flow, the contrast used for obtaining CT angiogram does not reach the level of occlusion and thus the occlusion appears to be extracranial on the conventional CT angiogram²⁰. The only way to confirm the diagnosis of pseudoextracranial occlusion is to obtain an angiogram using fluoroscopy in the angio suite. Such cases form a significant number of patients presenting with extracranial occlusion who may benefit from the thrombectomy procedure, but are excluded from the trial based on the appearance on CT angiogram. Including cases with extracranial ICA occlusion on CTA will allow for enrollment of these patients. Randomized controlled trials such as ESCAPE and REVASCAT reported 40 (12.7%) and 31 (10.3%) patients with extracranial ICA occlusions. EXTEND-IA in early window and DEFUSE 3 in late time window also allowed for inclusion of patients with extracranial ICA, though did not report the number of patients enrolled with extracranial ICA.

2. Study Question, Aim, and Hypothesis

Study aims: are to evaluate in acute ischemic stroke patients due to a large vessel occlusion in the anterior circulation (MCA M1 and ICA):

- Primary aim: If thrombectomy plus medical management as compared to medical management alone will be efficacious and safe in patients with large core on either CT (ASPECTS 3-5) or perfusion imaging (CTP: rCBF<30% or MRP: ADC <620 ≥50cc), treated within 0-24 hours from last known well. We hypothesize that patients with unfavorable profiles (large core) treated with thrombectomy on either imaging modality will have significantly better outcomes than large core patients treated with medical management only.
- Second aim: The second aim is to look at the correlation of imaging profiles with thrombectomy clinical outcomes and treatment effect. It will be evaluated by comparing the outcomes in patients with discordant imaging profile and assessing if thrombectomy outcome rates and treatment effect will differ in patients with

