3.7. Outcome Measures

3.7.1.1. Primary Outcome

The primary outcome #1 will be the distribution of mRS scores at 90 days. The primary outcome #2 will be the percentage of good outcome (mRS 0-2) at 90 days. The definition of favorable primary clinical outcomes is the patients' functional outcomes at 90 (+/- 15) days, measured by a modified Rankin scale (mRS) score of 0-2. The determination of mRS scores will be performed by certified raters unaware of the treatment arm or the baseline clinical and radiographic characteristics of the individual patient by in person interview or by telephone if in-person visit is not possible.

The shift in the modified Rankin Scale score is better equipped to capture potential improvement in the functional outcomes as compared to a binary (dichotomized) outcome with intervention. Since the study population is composed of acute stroke patients with significant ischemic changes (unfavorable imaging profiles), the potential shift across modified Rankin Scale Score categories, not only the functional independence, is of clinical significance. For details, a change of mRS score of 5 – completely bedridden to mRS score of 4 – ambulating with a wheelchair and to mRS score of 3 – ambulating with a cane is a successful outcome for thrombectomy. We will still have the dichotomized outcome as our second primary outcome.

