This distribution corresponds to a standardized effect of 0.34 for the primary analysis. Based on these data, the fixed sample size for a non-adaptive design requires a total of 376 patients (188/arm) to have 90% power at an alpha of 5% (Wilcoxon-Mann-Whitney test); We add additional 184 patients for the adaptive design to reach a maximum sample size of 560. We will conduct two interim analyses when we reach the number of patients at 200 and 380. Through extensive simulation studies, we have shown that with 560 patients in total for the adaptive design, we will have around 91% power to test for a standardized effect size of 0.34 in the overall population (assuming homogeneous EVT effect across six disjoint groups) by controlling an overall (one-sided) Type I error rate at 2.5%.

Efficacy and futility bound At each analysis (two interim analyses and the final analysis), an efficacy bound will be set to decide if the study should be stopped for efficacy while controlling the overall (one-sided) Type I error rate at 2.5%. At each interim analysis, a futility bound will be set to decide if the study should continue recruitment in the overall group, shift accrual and testing to a subgroup, or stop the trial entirely. When the futility bound is crossed and the optimal subgroup is selected, the maximum analyzed sample size will not be fixed but a random variable (smaller than the fixed maximum sample size 560). Due to the reduction in the maximum number of patients available for analysis at the end of the study, our design allows

an easier futility stop after subgroup selection. Further details regarding efficacy and futility bounds at interim and final analyses is provided in Appendix B.

First interim analysis (n=200 randomized and completed 90-day follow-up): The null hypothesis is tested in the entire patient cohort:

1. If neither efficacy nor futility bound is crossed, the trial continues enrollment to the 2nd interim analysis.
2. If the efficacy bound is crossed, the trial stops and efficacy is declared in the overall cohort.
3. If the futility bound is crossed, the optimal subgroup is selected based on the GLR statistic and the null hypothesis is tested in this selected subgroup:
 - 3.1. If neither bound is crossed, the trial will continue with enrollment limited to the selected subgroup
 - 3.2. If the efficacy bound is crossed, the trial stops and efficacy is declared in the selected subgroup

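### Appendix B's Wilcoxon rule is signed the wrong way: with ordinary ranks it claims efficacy when thrombectomy patients have higher (worse) mRS scores

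*Combined protocol and SAP*

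**What the plan says.** Section 6.1 names a normal approximation to the Wilcoxon-Mann-Whitney test and lists the action at each analysis. For the bounds it refers elsewhere: "Further details regarding efficacy and futility bounds at interim and final analyses is provided in Appendix B". Appendix B is the only place that gives the formulas and cut-offs.

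- **Statistic.** W is defined to "be the sum of the ranks of Rankin scores from the endovascular group". Z is W minus its null mean, divided by its null SD. The futility statistic Z-tilde also subtracts n·n0·theta from the numerator, where n and n0 are the thrombectomy (EVT) and medical management (MM) arm sizes.
- **Efficacy.** "we will terminate the trial and claims efficacy for the endovascular group if the following efficacy bound is crossed", which is Z ≥ 2.604 at an interim look and Z ≥ 2.772 at the final analysis.
- **Futility.** Z-tilde ≤ -1.897.
- **Enrichment.** After futility in the whole population, the subgroup "with the largest value of" Z is chosen.
- **Hypotheses.** The null is P(Y ≤ X) = 1/2 and the alternative is P(Y ≤ X) = 1/2 + theta, with theta = 0.0791. Y "denotes the Rankin score in the medical management group and X denotes the Rankin score in the endovascular group".

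On the direction of the scale, Section 3.7.1.1 describes moving from mRS 5 to 4 to 3 and says that "ambulating with a cane is a successful outcome for thrombectomy". Section 6.5 codes death as mRS 6. Section 2 hypothesises that thrombectomy patients "will have significantly better outcomes than large core patients treated with medical management only".

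**The concern.** Ordinary ranks ascend with the score. A large W, and so a large positive Z, then means that the thrombectomy arm has the higher Rankin scores, which on this scale are the worse outcomes. The alternative in Appendix B says the same: X, the thrombectomy score, tends to be at least as large as Y. No section states descending ranks or a reversed score.

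All three decisions inherit the sign. A program built literally from the text would send an effective treatment to futility, restrict enrolment to the subgroup in which thrombectomy looks worst, and could declare harm as efficacy. The test is one-sided at 2.5%, so the direction is part of the hypothesis and cannot be settled after the data are seen.

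**Working it through.** **Inputs.** The projected 90-day mRS percentages for scores 0 to 6 in Section 6.1 are EVT 4/8/12/16/19/13/28 and MM 1/4/9/14/19/10/43. Appendix B gives looks at 200, 380 and 560 patients, the bounds 2.604, -1.897 and 2.772, one-sided alpha 0.025 and power 0.9. Allocation is 1:1.

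**1. The plan's own figures reproduce.** theta = (1.960 + 1.2816)/√(3 × 560) = 0.0791, as stated. The fixed-design sample size also reproduces, with thrombectomy lowering the mRS: (1.960 + 1.2816)² × 0.9421/(3 × 0.09375²) = 375.4, so 376. Here 0.9421 is the tie correction from the pooled table and 0.09375 comes from step 2.

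**2. Direction of the projected effect.**
- P(EVT < MM) = 0.04×0.99 + 0.08×0.95 + 0.12×0.86 + 0.16×0.72 + 0.19×0.53 + 0.13×0.43 = 0.4906
- P(tie) = 0.2063
- P(EVT > MM) = 1 - 0.4906 - 0.2063 = 0.3031
- Mid-rank probability that EVT is higher: 0.3031 + 0.2063/2 = 0.40625, below 1/2
- Mid-rank probability that EVT is lower: 0.59375, which is 1/2 + 0.09375

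**3. The parts of Appendix B agree only on ascending ranks.** With ascending mid-ranks,

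W - n(n + n0 + 1)/2 = n·n0·[P(Y < X) + ½P(Y = X) - ½].

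Subtracting n·n0·theta in Z-tilde therefore matches the stated alternative, ties aside, only if ranks ascend. If descending ranks were meant, Z and Z-tilde would be right, but the stated alternative would be reversed.

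**4. The written rule on the projected table, 100 per arm.**
- W = 9112.5 and its null mean is 100 × 201/2 = 10050, a difference of -937.5 = 100 × 100 × (0.40625 - 0.5)
- SD = √(100 × 100 × 201/12) = 409.3
- Z = -937.5/409.3 = -2.29
- Z-tilde = (-937.5 - 791)/409.3 = -4.22, well beyond -1.897

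| Patients | Z as written | Z-tilde as written | Z reversed | Z-tilde reversed |
|---|---|---|---|---|
| 200 | -2.29 | -4.22 | +2.29 | +0.36 |
| 380 | -3.16 | -5.83 | +3.16 | +0.49 |
| 560 | -3.84 | -7.08 | +3.84 | +0.60 |

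**5. Simulation of the overall-population stage only** (5,000 trials per case, mid-ranks, Appendix B variance).

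| Truth | Ranks | Efficacy claimed | Futility crossed, look 1 | Futility crossed, look 2 |
|---|---|---|---|---|
| Projected benefit | as written | 0% | 99.2% | 0.8% |
| Same-sized harm (arms swapped) | as written | 89.3% | 0.8% | 0.4% |
| Projected benefit | reversed | 88.9% | 1.1% | 0.3% |

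**6. Simulation with the subgroup stage added** (group shares 14/6/14/6/42/18% from Section 6.1, theta held fixed after selection, 5,000 trials). Under the projected benefit the written rule claims efficacy in 2 trials (0.04%). Same-sized harm is declared efficacious in 91.0%. With the sign reversed, power is 89.9% with the Appendix B variance and 91.6% with a tie-corrected variance. Section 6.1 states: "we will have around 91% power to test for a standardized effect size of 0.34 in the overall population".

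**Limit of step 6.** With the correct sign, the null runs do not reproduce the null row of Table 3 (59.1% futility stops, average 426 randomised). They give 37–41% and 467–478 with theta fixed. With theta rescaled to the remaining maximum sample size, an assumption about the relaxed bound that Appendix B does not write out, they give 45–51% and 447–461. The result on direction is the same under both settings.

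**The case against.** The strongest reply is that Appendix B is silent on rank order rather than wrong. If the lower mRS receives the higher rank, the efficacy rule, the futility rule and the subgroup choice are all correct as printed, with no change to any bound. The rest of the protocol makes the intended direction plain: the hypothesis, the definition of success and the projected table all have thrombectomy lowering the mRS. On that view only the line stating the alternative is wrong, and that line is loose anyway. For a discrete score P(Y ≤ X) is not 1/2 under no effect. It is about 0.59 with the thrombectomy distribution in both arms and 0.63 with the medical one, and under the projected benefit it is 0.3031 + 0.2063 = 0.509. The score coding might also be given in the design paper that Appendix B cites, which is not available here.

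Much of this stands. The intent is not in doubt, the program may well be right, and the stated sample size and bounds do not depend on the sign. The simulated percentages describe a literal implementation that nobody has shown to exist. What does not stand is that the text can be left alone. Descending ranks rescue Z but leave the written alternative reversed, so Appendix B needs correcting on either reading. A prespecified one-sided rule should not need its sign inferred from other sections.

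**Conclusion.** The concern holds and must be fixed. As written, with ordinary ascending ranks, the confirmatory rule for stopping and enrichment runs opposite to the trial's hypothesis. Under the plan's own projected benefit, its Z is expected at -2.29, -3.16 and -3.84 at the three analyses. That direction is exact algebra from the projected table and rests on no simulation. The simulated size (efficacy claimed in essentially no trials under benefit, and in about 90% under same-sized harm) assumes a program that follows the text literally and, where the subgroup stage is included, a chosen treatment of theta after selection.

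This is an error in the specification. It is not evidence that the analysis program is wrong. The sample size, theta and bounds are unaffected.

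**What to change.** In Appendix B:

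1. State that ranks are assigned so that a lower mRS gets the higher rank (or use -Z), and apply this to Z, Z-tilde and the subgroup selection.
2. Restate the hypotheses as P(X < Y) + ½P(X = Y) = 1/2 versus 1/2 + theta, with X the thrombectomy score and Y the medical management score. The half-tie term is needed because about 21% of pairs tie.
3. Verify the interim-analysis program against the corrected text. A simple test is the projected table at 100 per arm, which with mid-ranks and the present variance should return Z = +2.29 and Z-tilde = +0.36.

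This costs some rewording and a program check. No patients are added, and 2.604, -1.897, 2.772, theta and 560 stay as they are.

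Optional and secondary: state that mid-ranks are used and adopt the tie-corrected variance. The present variance ignores ties and is only conservative, with simulated type I error of 1.4–1.9% against 2.2–2.3% tie-corrected (theta fixed), and a power loss of under 2 points. If the variance is changed, the bounds should be re-verified with one re-run of the boundary simulation.
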